#### **6.2.5. Median and Confidence Interval Estimation Methods**

Hodges Lehmann estimation will be used to provide estimators of the median and 95% CIs for the median.

#### **6.2.6. Dose Trend Methods**

The Joncheere-Terpstra (JT) approach will be used to provide an estimate of relationship between change in LDLc from DB Baseline to Week 16 and dose level.

Example SAS code as follows:

```
ODS graphics on;  
proc freq data=ldlchg;  
    Tables trt*chg/out=jtpval jt;  
    Title1 "Jonckheere-Terpstra Trend Test for Continuous Data";  
Run;  
ODS graphics off;
```

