### 6.2.3. Analysis of Covariance

Analysis of covariance (ANCOVA) will be performed to provide least squares (LS) mean estimates and 95% confidence intervals (CIs) of the change and percentage change from Baseline at each DB post-Baseline visit. Model covariates will include the randomization stratification values (ie, pre-randomization fasted serum LDLc [ $\leq 125$  mg/dL or  $> 125$  mg/dL] and baseline fibrosis stage [stage 1, 2 or stage 3, 4]) and the Baseline value of the parameter being evaluated. The primary analysis will exclude the treatment by visit interaction term.

Example SAS code for the primary analysis is as follows:

ODS graphics on;

```
proc mixed data=ADEFF noclprint plots=residualpanel;
```

```
by visit;
```

```
class ldlcon fbstg trt;
```

```
model change=Baseline ldlcon fbstg trt / ddfm=kr;
```

```
lsmeans trt / cl diff alpha=0.05;
```

```
title1 "Linear Mixed Effects Model Based Estimates of XXXX Means by Visit";
```

```
title2 " Fixed Effects for Visit, Randomization Strata and Baseline as Covariates";
```

```
run;
```

```
ODS graphics off;
```

```
quit;
```

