## **9. EFFICACY ANALYSES**

The primary and secondary efficacy analyses will be based on the EE Population. Analyses on the ITT Population will only be performed if greater than 20% of ITT subjects are excluded in the EE Population. All analyses are to be carried out on observed data, as there are no imputations planned. The efficacy data are a result of the centralized, specialized nuclear magnetic resonance (NMR) lipoprotein assay and the central laboratory serum chemistry. All analyses of lipoprotein metabolism will include fasted samples only. For all lipoprotein concentration values, the serum chemistry panel results will be used. For particle size and particle concentration, the NMR lipoprotein assay results will be used. Sensitivity analysis may be performed with the NMR lipoprotein concentration results.

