### **9.1. Primary Efficacy Analyses**

The primary efficacy analysis, changes in LDLc, LDLs, and LDLpc at Week 16 (end of DB) from Baseline will be summarized by treatment group, using the EE Population.

The observed values, change from Baseline, and percentage change from Baseline will be summarized by treatment group and visit using arithmetic summary statistics as described in [Section 6.2.1](#).

In order to provide estimates of the change from Baseline and corresponding 95% CI, the ANCOVA methods described in [Section 6.2.3](#) will be applied with change from Baseline as the dependent variable, including treatment group, and randomization stratification factor as fixed effects and Baseline as a covariate. The same analysis will be carried out using percentage change from Baseline as the dependent variable. Model fit will be assessed in order to determine the validity of the estimates. Estimates of LS means, SEs, and 95% CIs will be presented by treatment group.

The comparison of LDLc, LDLs, and LDLpc change from baseline and percentage change from baseline values between each active treatment group and placebo group at each DB post-Baseline visit will be performed as exploratory analyses. Estimates of the LS mean difference

between each active treatment group and placebo group, the SE of the difference, and 95% CI of the difference will be presented.

The relationship of OCA dose level and changes in LDLc will be explored using the Jonckheere-Terpstra (JT) test.

Sensitivity analysis for the primary efficacy analysis will be performed using the ITT Population using both the ANCOVA methods described in [Section 6.2.3](#) and the ANCOVA with repeated measures methods described in [Section 6.2.4](#).

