## APPENDIX A. LIST OF TABLES, FIGURES, AND LISTINGS

### List of Tables

Table Number	Population	Table Title
14.1		Demographic Data
14.1.1	All Randomized Subjects	Summary of Analysis Populations
14.1.2.1	All Randomized Subjects	Summary of Subject Disposition
14.1.2.2	ITT	Summary of Investigational Product Discontinuation
14.1.2.3	ITT	Summary of Study Medication Discontinuation
14.1.3	ITT	Summary of Subject Protocol Deviations
14.1.4.1	ITT	Summary of Demographics and Baseline Characteristics
14.1.4.2	PK	Summary of Demographics and Baseline Characteristics
14.1.4.3	EE	Summary of Demographics and Baseline Characteristics (only produced if > 20% of ITT subjects are excluded from EE population)
14.1.5.1	ITT	Summary of NASH Disease History
14.1.5.2	EE	Summary of NASH Disease History
14.1.6	ITT	Summary of Tobacco Use Score
14.1.7	ITT	Summary of Statin History
14.1.8	ITT	Summary of Family Cardiovascular History
14.1.9	ITT	Summary of Abnormal Medical History at Baseline
14.2		Efficacy Data
14.2.1.1.1	EE	Summary of LDL Cholesterol Concentration – SI Units
14.2.1.1.2	EE	Summary of LDL Cholesterol Concentration – CV Units
14.2.1.1.3	EE	Summary of LDL Cholesterol Particle Size and Particle Concentration
14.2.1.2.1	ITT	Summary of LDL Cholesterol Concentration – SI Units
14.2.1.2.2	ITT	Summary of LDL Cholesterol Concentration – CV Units
14.2.1.2.3	ITT	Summary of LDL Cholesterol Particle Size and Particle Concentration
14.2.1.3.1	ITT	Summary of LDL Cholesterol Concentration – SI Units (MMRM)
14.2.1.3.2	ITT	Summary of LDL Cholesterol Concentration – CV Units (MMRM)
14.2.1.3.3	ITT	Summary of LDL Cholesterol Particle Size and Particle Concentration (MMRM)
14.2.1.4.1	ITT	Summary of Change in LDL Cholesterol Concentration and Relationship to Treatment – CV Units
14.2.1.4.2	ITT	Summary of Change in LDL Cholesterol Concentration and Relationship to Treatment – SI Units
14.2.2.1.1	EE	Summary of HDL Cholesterol Concentration – SI Units
14.2.2.1.2	EE	Summary of HDL Cholesterol Concentration – CV Units
14.2.2.1.3	EE	Summary of HDL Cholesterol Particle Size and Particle Concentration

Table Number	Population	Table Title
14.2.2.2.1	ITT	Summary of HDL Cholesterol Concentration – SI Units (MMRM)
14.2.2.2.2	ITT	Summary of HDL Cholesterol Concentration – CV Units (MMRM)
14.2.2.2.3	ITT	Summary of HDL Cholesterol Particle Size and Particle Concentration (MMRM)
14.2.3.1.1	EE	Summary of V:DL Cholesterol Concentration – SI Units

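### The only formal dose-trend test for LDLc uses raw Week 16 change, unadjusted for Baseline LDLc and the randomisation strata; it is valid but can lose precision, gives no estimate with a CI, and is listed for ITT only

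*SAP*

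**What the plan says.** - **Trend test.** Section 6.2.6 applies the JT test to the "relationship between change in LDLc from DB Baseline to Week 16 and dose level". Its example code is a two-way table, "Tables trt*chg/out=jtpval jt", with no Baseline covariate and no stratum variable. Section 9.1 gives it one sentence: "The relationship of OCA dose level and changes in LDLc will be explored using the Jonckheere-Terpstra (JT) test". That sentence names no population.
- **LDLc models.** Section 6.2.3 states: "Model covariates will include the randomization stratification values". The parameter's Baseline value is also included, and the code reads "model change=Baseline ldlcon fbstg trt / ddfm=kr". The repeated-measures model in Section 6.2.4 uses the same adjustment.
- **Population.** Section 9 states: "The primary and secondary efficacy analyses will be based on the EE Population". It adds: "Analyses on the ITT Population will only be performed if greater than 20% of ITT subjects are excluded" from EE. Section 9.1 then plans ITT sensitivity analyses without that condition, but only for the two ANCOVA models.
- **Tables.** Appendix A lists 14.2.1.4.1 and 14.2.1.4.2, "Summary of Change in LDL Cholesterol Concentration and Relationship to Treatment", under ITT. No EE version is listed.
- **Status of p-values.** Section 6.2.8 treats all CIs and p-values as descriptive and makes no multiplicity adjustment.

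**The concern.** The sponsor already treats starting LDLc as prognostic: it stratifies randomisation at 125 mg/dL and puts Baseline LDLc into every LDLc model. The trend test is the one formal LDLc analysis that leaves it out. If change is correlated with Baseline, that variation stays in the noise and the dose trend is seen less sharply than the collected data allow.

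Two smaller matters go with this. Section 6.2.6 promises an estimate of the relationship, but the JT code returns a test statistic and a p-value. A descriptive study is better served by a size in mg/dL with an interval. And the trend sits under the EE primary analysis in Section 9.1 while its apparent tables are ITT, so a reader cannot set the trend beside the primary EE dose-group means on the same subjects.

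**Working it through.** **1. The plan's own power figure.** Section 5 gives a 22 mg/dL rise, SD 24, n = 20 and two-sided 0.05. For a one-sample t-test the noncentrality is 22 / (24/√20) = 4.10, and the noncentral t gives 97.29%, in line with the stated 97.3%. That figure is for a within-group change. The SAP states no power for the dose trend, so the rest needs assumptions.

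**2. Inputs for the trend.** From the SAP: four equal arms, 20 per arm, SD 24, two-sided 0.05. Assumed, because the SAP gives neither: the dose-group means and the correlation ρ between Baseline LDLc and change.

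**3. Closed-form check.** Take means of 0/5/10/15 and equal-step weights (-3, -1, 1, 3).
- Contrast = -3(0) - 5 + 10 + 3(15) = 50.
- Unadjusted SE = 24 × √((9+1+1+9)/20) = 24.
- Adjusting for Baseline multiplies the SE by √(1-ρ²).
- Power ≈ Φ(50/SE - 1.96).

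| ρ | SE | 50/SE | Approximate power |
|---|---|---|---|
| 0 (same as unadjusted) | 24.0 | 2.08 | 55% |
| -0.3 | 22.9 | 2.18 | 59% |
| -0.5 | 20.8 | 2.41 | 67% |
| -0.6 | 19.2 | 2.60 | 74% |

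A confidence interval would be narrower by 1 - √(1-ρ²): about 5%, 13% and 20% at these three non-zero correlations.

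**4. Simulation, same means.** With 3000 trials per case (Monte Carlo SE at most √(0.25/3000) = 0.9 points), unadjusted JT power is 51-52%. The adjusted trend has 57%, 65% and 72% at ρ = -0.3, -0.5 and -0.6. At ρ = 0 a repeat run gave 51% against 53%. These sit slightly below the closed form, which ignores the efficiency cost of ranks and the degrees of freedom spent on strata.

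**5. Other shapes.** Here the Section 5 figure of 22 mg/dL is taken, as an assumption, for the difference between 25 mg and placebo. Power is shown as unadjusted JT / adjusted ANCOVA trend contrast, n = 20 per arm:

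| Means (mg/dL) | ρ = 0 | -0.3 | -0.5 | -0.7 |
|---|---|---|---|---|
| 0/4.4/8.8/22 | 0.81 / 0.82 | 0.81 / 0.85 | 0.80 / 0.91 | 0.81 / 0.98 |
| 0/7.3/14.7/22 | 0.84 / 0.86 | 0.84 / 0.88 | 0.84 / 0.93 | 0.85 / 0.99 |
| 0/22/22/22 | 0.72 / 0.77 | 0.73 / 0.80 | 0.71 / 0.87 | 0.72 / 0.96 |

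**6. Validity.** With no dose effect, the unadjusted JT rejects in 4.7% to 5.7% of trials across all ρ, at 20 or 16 per arm.

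**7. Population.** ITT has at least as many subjects as EE. With means 0/4.4/8.8/22 and ρ = 0, the JT has power 0.81 at 20 per arm and 0.70 at 16 per arm (assuming 20% are excluded from EE). The mismatch is therefore one of alignment, not of power.

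**The case against.** The JT test is a legitimate, covariate-free rank test, it keeps its error rate, it is labelled exploratory, and no decision depends on its power. The size of any gain rests on a correlation and a dose-response shape that the SAP does not give. All subjects start atorvastatin at Week 4, which makes the Week 16 correlation harder to guess. All of this stands, and it is why the point is minor.

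Several stronger readings are tempting, and the SAP does not support them:

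- *The trend test is simply weaker than the primary analysis.* At zero correlation adjustment gains little or nothing. The primary analysis also estimates group means and is not a trend test. With evenly spaced means and ρ = 0, the unadjusted JT (0.84) is slightly ahead of the adjusted 25 mg versus placebo comparison (0.81).
- *Using ITT weakens it.* ITT is at least as large as EE.
- *It is the only view of dose.* Section 9.1 also gives adjusted LS means by dose and adjusted differences from placebo, and Section 10.4 plots LDLc against exposure. The JT is the only formal trend test.
- *It has no matching dose-group means.* Section 9.1 and Appendix A provide ITT ANCOVA and repeated-measures results for LDLc. What is missing is an EE trend.
- *The code puts the doses in the wrong order.* The code shown sets no order option and does not say how the treatment variable is coded. That leaves a gap in the specification, with no evidence of miscoding.

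The titles of tables 14.2.1.4.1-2 do not name the JT test. The link is inferred because no other listed table fits.

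**Conclusion.** The point holds as a modest efficiency and alignment improvement. The unadjusted JT is valid. Where change correlates with Baseline it gives up precision that data already collected would supply: about 6, 14 and 21 points of power (51% against 57%, 65% and 72%) at correlations of -0.3, -0.5 and -0.6, and little or nothing at zero. Those figures rest on assumed effects of 0/5/10/15 mg/dL, with SD 24 and 20 per arm. With a 22 mg/dL top-dose effect the gain is smaller at weak correlation (4 points at -0.3 when means are proportional to dose) and still material at -0.5 (11 points, 0.80 to 0.91).

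Two parts do not depend on those assumptions. The JT as specified gives no effect estimate with an interval, and its population is unnamed in Section 9.1 while its apparent tables are ITT only.

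**What to change.** 1. In Sections 6.2.6 and 9.1, add an ordered-dose contrast (placebo < 5 < 10 < 25 mg) at Week 16 in the Section 6.2.3 ANCOVA, adjusted for Baseline LDLc and both strata, and report it with its 95% CI. Fix the weights in advance. With the equal-step weights (-3, -1, 1, 3) used above, dividing the contrast by 10 gives mg/dL per dose step; for means 0/5/10/15 that is 50/10 = 5.
2. Keep the unadjusted JT as a supplement.
3. Run the trend in EE, the primary population, as well as in ITT. Name both in Section 9.1, add EE versions of tables 14.2.1.4.1-2, and name the method in the titles. Section 9's condition on ITT analyses should then allow for the ITT version.
4. State the dose order explicitly in the JT code, for example with a numeric dose variable, as a safeguard.

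The cost is a few lines of code, some SAP wording and additional table versions. No new data are needed.

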### **6.2.7. Geometric (Natural Log Transformed) Summaries**

To calculate a geometric mean and corresponding 95% CI, the following steps are used:

- Transform the data by taking natural logarithms ( $\log_e$ )
- Calculate the mean and 95% CI of the  $\log_e$ -transformed data
- Exponentiate the mean and the lower and upper CIs back to the original scale to obtain the geometric mean and corresponding 95% CI

### **6.2.8. Multiple Comparisons/Multiplicity**

As this is a descriptive study, no formal adjustments for multiple comparisons are being made. Therefore, CIs and p-values will be interpreted as purely descriptive.

### **6.2.9. Subgroup Analyses**

The following subgroups will be assessed for some specific endpoints as noted.

Diabetes status (Yes/No) – defined as subjects with any condition in the Endocrine/Metabolic body system and medical term is coded to ‘Type 2 diabetes mellitus’.

Antihypertensive medication use (Yes/No) – Anatomical Therapeutic Chemical (ATC) codes starting with ‘C02’; for blood pressure endpoints.

Prior statin medication use (Yes/No) – collected on eCRF Statin Use History; for lipoprotein evaluations.

If less than 10% of the ITT population subjects are not included in a subgroup, the subgroup analysis will not be performed.

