## **4. STUDY DESIGN AND PLAN**

This is a Phase 2, double-blind, randomized, placebo-controlled, multicenter study, evaluating the effects of OCA, and the subsequent addition of statin therapy, on lipoprotein metabolism in subjects with NASH with fibrosis stage 1 to 4, but no evidence of hepatic decompensation, in the DB phase, followed by an open-label LTSE phase to evaluate long term safety and efficacy.

Approximately 80 subjects with histological evidence of definite or probable NASH, who meet all inclusion and none of the exclusion criteria will be enrolled in the study. The histological evidence of definite or probable NASH will be based on the central read of a liver biopsy obtained no more than 1 year prior to randomization and a nonalcoholic fatty liver disease activity score (NAS) of 4 or greater. Subjects not using statin therapy (ie, statin-free) and statin-treated subjects may be enrolled. Statin-treated subjects will be required to stop statin treatment (after signing informed consent) for up to 5 weeks, including a 4-week statin washout period, prior to Randomization/Day 1.

Subjects will have a screening period of up to 5 weeks prior to Randomization/Day 1. At the Randomization (Day 1) Visit, subjects will be randomized in a 1:1:1:1 ratio to receive OCA 5 mg, OCA 10 mg, OCA 25 mg, or placebo, orally, once daily, for 16 weeks. Randomization will be stratified by the pre-randomization fasting serum LDLc ( $\leq$ 125 mg/dL or  $>$ 125 mg/dL) and baseline fibrosis stage (stage 1, 2 or stage 3, 4).

[figure not shown]
Subjects will attend on-site clinic visits at Weeks 2, 4, 8, 12, and 16 and will be contacted at Weeks 6, 10 and 14 to assess safety and treatment compliance. At the Week 4 Visit, all subjects will initiate treatment with atorvastatin at a dose of 10 mg once daily. At the Week 8 Visit, atorvastatin will be increased to 20 mg once daily (if 10 mg daily is tolerated), and continued for an additional 4 weeks. After 4 weeks of treatment at 20 mg, the atorvastatin dose may be titrated (up or down) as clinically indicated. The final visit during the DB phase will occur at Week 16, after which subjects may continue into the open-label LTSE.

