### 6.3.6. Cardiovascular Risk Scores Calculations

Cardiovascular risk scores (ie, FRS and Reynolds) will be calculated at the time of data analysis using data collected via the Baseline Tobacco Use, Family Cardiovascular History eCRFs, and the central laboratory data. The calculations are as follows:

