#### FRS:

The 10-year cardiovascular disease risk (%) for women =  $[1 - 0.95012^{\exp(B - 26.1931)}] \times 100\%$ , where

$B = 2.32888 \times \text{natural logarithm (age)} + 1.20904 \times \text{natural logarithm (total cholesterol)} - 0.70833 \times \text{natural logarithm (high-density lipoprotein cholesterol)} + 2.76157 \times \text{natural logarithm (systolic blood pressure if not treated)} + 2.82263 \times \text{natural logarithm (systolic blood pressure if treated)} + 0.52873 \text{ (if current smoker)} + 0.69154 \text{ (if diabetic)}$

The 10-year cardiovascular disease risk (%) for men =  $[1 - 0.88936^{\exp(B - 23.9802)}] \times 100\%$ , where  $B = 3.06117 \times \text{natural logarithm (age)} + 1.2370 \times \text{natural logarithm (total cholesterol)} - 0.93263 \times \text{natural logarithm (high-density lipoprotein cholesterol)} + 1.93303 \times \text{natural logarithm (systolic blood pressure if not treated)} + 1.99881 \times \text{natural logarithm (systolic blood pressure if treated)} + 0.65451 \text{ (if current smoker)} + 0.57367 \text{ (if diabetic)}$  [Framingham Heart Study 2016].

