## **8.3. Demographic and Baseline Characteristics**

Demographic variables will include the following:

- Age at informed consent
- Age at informed consent categorized as < 65 years and  $\geq$  65 years
- Sex
- Race/ethnicity

Other Baseline characteristics will include the following:

- Weight (kg)
- Height (cm) at Screening visit
- BMI ( $\text{kg}/\text{m}^2$ )
- BMI categorized as < 30  $\text{kg}/\text{m}^2$  and  $\geq$  30  $\text{kg}/\text{m}^2$
- Liver fibrosis stage using NASH Clinical Research Network (CRN) scoring criteria categorized as Stage 1a, 1b, 1c, 2, 3, 4
- Liver fibrosis stage using NASH CRN scoring criteria categorized as Stage 1, 2 and Stage 3, 4
- Liver fibrosis stage using modified Ishak scoring criteria categorized as Stage 1, 2, 3, 4, 5, 6
- NAFLD Activity Score (NAS) and its components categorized as:
  - Steatosis: 0, 1, 2, 3
  - Hepatocellular Ballooning: 0, 1, 2
  - Lobular Inflammation: 0, 1, 2, 3
- NAS categorized as < 6 and  $\geq$  6 total points
- Diabetes status: Yes, No (defined as subjects with any condition in the Endocrine/Metabolic body system and medical term containing “diabetes type II” or

similar derivative, as collected on the eCRF Medical History; if unable to determine what type of diabetes, set diabetes status to yes)

- Concomitant medication use (ongoing on Day 1. If it cannot be determined whether the medication was ongoing at the Day 1 visit due to a partial start or stop date, then it will be counted as ongoing.)
  - Vitamin E (ATC codes = 'A11HA' and Trade name = 'E VITAMIN')
  - TZD (ATC codes starting with 'A10BG')
  - Antidiabetic medication (ATC codes starting with 'A10')
  - Antihypertension medication (ATC codes starting with 'C02')
- Screening fasted serum LDL cholesterol concentration categorized as  $\leq$  and  $> 125$  mg/dL
- Screening HDL cholesterol concentration (mg/dL) categorized as  $\geq$  lower limit of normal (LLN),  $<$  LLN
- Baseline liver function test results as a continuous variable and categorized as follows by the LLN and the upper limit of normal (ULN) unless otherwise specified:
  - ALT:  $\leq 40$  U/L,  $> 40$  U/L and  $\leq$  ULN,  $>$  ULN
  - AST:  $\leq 40$  U/L,  $> 40$  U/L and  $\leq$  ULN,  $>$  ULN
  - Direct Bilirubin:  $\leq$  ULN,  $>$  ULN
  - Total Bilirubin:  $\leq$  ULN,  $>$  ULN
  - Platelets:  $\geq$  LLN,  $<$  LLN

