## **8.10. Prior and New Concomitant Medications**

Verbatim terms on eCRFs will be mapped to ATC class and preferred term using the World Health Organization Drug Dictionary Enhanced (WHODDE; WHO-DDE-B2 Dec2015).

Pretreatment medications are those medications with start and stop dates prior to the first dose of investigational product in the DB phase. Prior concomitant medications are those medications started prior to, and continued after, the first OCA dose in the DB phase. New concomitant

medications are those medications that were started after the first OCA dose in the DB phase. If it cannot be determined whether the medication was a new concomitant medication due to a partial start or stop date or if the medication is taken on the same date as the first OCA dose in the DB phase, then it will be counted as a new concomitant medication.

Pretreatment medications will be presented in listings only. Prior and new concomitant medications will be summarized by World Health Organization ATC class and preferred term using the ITT Population. New concomitant medications will be summarized separately. These summaries will present the number and percentage of subjects using each medication. Subjects may have more than 1 medication per ATC class and preferred name. A subject is counted once when 1 or more medications is reported at the ATC class or preferred term level. Each summary table will be ordered by descending order of incidence, for all OCA-treated subjects, of ATC class and preferred term within each ATC class.

Prior and new concomitant medications will be presented in a data listing.

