### **9.3.6. Anthropometric Measures and Blood Pressure**

Anthropometric measures (ie, body weight, waist and hip circumference measurements, BMI, and waist-to-hip ratio calculations) and blood pressure will be summarized using arithmetic summary statistics as described in [Section 6.2.1](#) at Baseline and at each DB post-Baseline visit. Change and percentage change from baseline will also be summarized in the same manner. Re-tests or unscheduled visit results after the first OCA dose administration time will not be summarized but will be included in the data listings.

Treatment groups will be compared using an ANCOVA model with change from Baseline as the dependent variable, including treatment group, and randomization stratification factors as fixed effects and baseline as a covariate. The same analysis will be carried out using percentage change from Baseline as the dependent variable. Estimates of LS means, SEs, and 95% CIs will be presented by treatment group. Estimates of the mean difference between each active treatment group and placebo group, the SE of the difference, and 95% CI of the difference will be presented.

Subgroup analyses will also be presented by diabetes status, excluding the randomization stratification factors from the ANCOVA model. Subgroup analyses of blood pressure will also be presented by use of antihypertensive medications.

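### Antihypertensive use is defined by ATC prefix C02 alone, so subjects on only diuretics, beta-blockers, calcium-channel blockers or renin-angiotensin agents count as non-users; 'treated' in the Framingham score is not defined

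*SAP*

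**What the plan says.** SAP section 6.2.9 lists the subgroup "Antihypertensive medication use (Yes/No) – Anatomical Therapeutic Chemical (ATC) codes starting with" C02, and limits it to blood pressure endpoints. Section 8.3 repeats the rule for the baseline table: "Antihypertension medication (ATC codes starting with 'C02". Two matching statements make this a rule, not a slip. No other section adds code groups or a review step.

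The flag is used in section 9.3.6: "Subgroup analyses of blood pressure will also be presented by use of antihypertensive medications". Appendix A lists the outputs as Tables 14.2.14.3 (EE Population) and 14.3.4.5.2 (Safety Population). Section 6.2.9 also has a size rule: "If less than 10% of the ITT population subjects are not included in a subgroup, the subgroup analysis will not be performed".

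ATC is the SAP's own coding standard. Section 8.10 states: "Verbatim terms on eCRFs will be mapped to ATC class and preferred term".

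The Framingham equations in section 6.3.6 use a separate coefficient for "natural logarithm (systolic blood pressure if treated"). The same section says the risk scores are calculated "using data collected via the Baseline Tobacco Use, Family Cardiovascular History eCRFs, and the central laboratory data". That list has no medication source, and 'treated' is not defined. Section 3.3.9 mentions medications among the score inputs but gives no code list.

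**The concern.** C02 is only one of several ATC groups that hold blood-pressure drugs. Diuretics are in C03, beta-blockers in C07, calcium-channel blockers in C08 and renin-angiotensin agents in C09. Programmed exactly as written, the rule returns 'No' for a subject whose only blood-pressure drug is in one of those four groups. In the same list in section 8.3, antidiabetic use is taken from the whole A10 group, so the evident aim is to capture a therapeutic class. The C02 prefix does not do that.

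Three things are at stake:
- The baseline row under-reports antihypertensive use.
- The two blood-pressure tables do not separate treated from untreated subjects, or are not produced at all.
- A programmer who needs a treated flag for the Framingham score finds only one antihypertensive definition in the SAP, and it is the C02 rule.

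Independent double programming (section 6.1) would not catch this, because the specification itself is at fault.

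**Working it through.** The SAP states no figure that depends on this definition, so there is nothing to reproduce. The checks below use its own coefficients and planned size. Every other input is marked as an assumption.

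**1. Classification.** A subject is 'Yes' if any drug has a C02 code. A subject on a C02 drug plus another class is still 'Yes'. The misclassified subjects are those treated with C03, C07, C08 or C09 drugs and no C02 drug. The SAP does not print the contents of the ATC groups; they are part of the coding standard it adopts.

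**2. Subgroup size and mixing.** Section 4 plans "Approximately 80 subjects with histological evidence of definite or probable NASH", so N = 80 and 10% of N is 8. Let p be the share of subjects truly on a blood-pressure drug and s the share of those with a C02 drug. Neither is in the SAP.

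- Yes = 80 × p × s
- No = 80 − Yes
- Truly treated share of No = (80p − Yes) / No

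| p (assumed) | s (assumed) | Yes | No | Truly treated share of No |
|---|---|---|---|---|
| 0.4 | 0 | 0 | 80 | 0.40 |
| 0.4 | 0.2 | 6.4 | 73.6 | 0.35 |
| 0.6 | 0 | 0 | 80 | 0.60 |
| 0.6 | 0.1 | 4.8 | 75.2 | 0.57 |
| 0.6 | 0.2 | 9.6 | 70.4 | 0.55 |
| 0.8 | 0 | 0 | 80 | 0.80 |
| 0.8 | 0.1 | 6.4 | 73.6 | 0.78 |
| 0.8 | 0.2 | 12.8 | 67.2 | 0.76 |

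Over this range the 'Yes' group has 0 to about 13 subjects. It reaches 8 only at s = 0.2 with p of 0.6 or 0.8.

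**3. Framingham score, conditional on the C02 flag being used there.** The equations have the form risk = 1 − S^E, with E = exp(B − constant). Scoring a treated subject as untreated divides E by k = exp(difference in coefficients × ln SBP). At SBP 140 (assumed):

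- Women: 2.82263 − 2.76157 = 0.06106, so k = exp(0.06106 × ln 140) = 1.352
- Men: 1.99881 − 1.93303 = 0.06578, so k = exp(0.06578 × ln 140) = 1.384

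Reported risk = 1 − (1 − true risk)^(1/k):

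| True risk | Women | Men |
|---|---|---|
| 20% | 15.2% | 14.9% |
| 30% | 23.2% | 22.7% |

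**4. Effect on change from Baseline, on the same condition.** Assume a diabetic, non-smoking woman aged 55 with total cholesterol 190 and HDL 45, whose SBP falls from 130 to 110. Scored as untreated, her risk goes from 12.06% to 7.78%. Scored as treated, it goes from 15.88% to 10.23%.

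- Absolute change: 7.78 − 12.06 = −4.28 points, against 10.23 − 15.88 = −5.65 points
- Percentage change: −4.28 / 12.06 = −35.5%, against −5.65 / 15.88 = −35.6%

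The level and the absolute change move. The percentage change barely does.

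**The case against.** **The ATC contents are not in the SAP.** True. But section 8.10 makes ATC the coding standard and the rule cannot be programmed without it. This is the meaning of the SAP's own codes, not a figure from a cited source. The classification point stands.

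**A reader might infer that the 'No' group holds most treated hypertensives.** The SAP gives no count by drug class and no share with a C02 drug. The ranges above are assumptions, so 'most' is not supported.

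**A reader might also infer that the Framingham scores will be understated.** The SAP does not say so. Section 6.2.9 limits the flag to blood pressure endpoints, and section 6.3.6 names no medication source. What is firm is narrower: 'treated' is undefined there. The 20% to 15% figure is a conditional illustration. Even on that path, section 9.3.7 plans descriptive summaries only, and percentage change is largely preserved if the same wrong status applies at every visit.

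**The two subgroup harms cannot both occur in full.** Correct. Either the analysis is dropped for size, or it is produced with a mixed 'No' group. Neither gives the comparison that section 9.3.6 intends.

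**The weight is limited.** Also correct. Blood pressure and the risk scores are exploratory, and section 6.2.8 treats all confidence intervals and p-values as descriptive.

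**Conclusion.** The point holds in a limited form. The C02-only rule in sections 6.2.9 and 8.3 gives a wrong classification when followed exactly. It affects one baseline row and two exploratory blood-pressure tables. The 'No' group mixes treated and untreated subjects, or the tables fall away under the apparent intent of the 10% rule if fewer than about 8 of 80 subjects take a C02 drug. How many subjects are misclassified cannot be found from the SAP.

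The missing definition of 'treated' in section 6.3.6 is a separate gap. If, and only if, the C02 flag filled it, the exponential term for a treated subject at SBP 140 would be understated by a factor of about 1.35 (women) or 1.38 (men).

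The conclusion rests on the ATC structure and on N of about 80. The primary LDL endpoints and their models do not use this flag. The change should be made, but the main result does not depend on it.

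**What to change.** Before database lock:

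- In sections 6.2.9 and 8.3, define antihypertensive use as any ATC code starting with C02, C03, C07, C08 or C09.
- Add a blinded medical or coding review of drugs in these groups that have other uses. The SAP does not show that the indication for each medication is recorded, so the rule should not depend on that field.
- In section 6.3.6, name this flag as the treated/untreated input to the Framingham score, and add concomitant medication data to the listed sources.

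The cost is a longer code list and a short review. Medications are already ATC-coded, so no new data are needed. The small downside is that some subjects who take these classes for other reasons may still be counted as users.
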